### 2.3.1.3 Listing for Abnormalities

Listings for ECG abnormalities by dosing, subject, and time-point will be provided for the following:

- Heart Rates
- PR-Interval
- QRS Duration
- QT-Interval
- First degree AV-Block
- Second degree AV-Block (Type 1)
- Second degree AV-Block (Type 2)
- Third-degree (complete) AV-Block

### 2.3.2 Echocardiograms

#### 2.3.2.1 Main Focus for Echocardiograms

The main focus for the echocardiographic analysis is the regurgitation score for the mitral and aortic valves at each time-point with the main focus being the development of clinically meaningful (pathologic) changes in valve regurgitation (definitions and thresholds defined below).

- Number of subjects who meet the FDA case definition of drug associated valvulopathy-aortic regurgitation  $\geq$  mild and/or mitral regurgitation  $\geq$  moderate
- Number of subjects with  $\geq$  trace mitral or aortic regurgitation at least one time post-baseline
- Number of subjects with  $\geq$  trace mitral or aortic regurgitation at end of study
- Number of subjects within each mitral or aortic regurgitation score by visit
- Number of subjects with clinically confirmed Valvular heart disease (VHD)

#### 2.3.2.2 Other Echocardiographic Analysis

Other, secondary endpoints include:

- Number of subjects within each tricuspid or pulmonic regurgitation score by visit
- Number of subjects with normal or trace tricuspid or pulmonic regurgitation at baseline and  $\geq$  mild tricuspid or pulmonic regurgitation at end of study
- Pulmonary Artery Systolic Pressure (PASP)
  - Mean change from baseline at end of study
  - Mean maximum change from baseline at anytime during therapy
  - Number of subjects with change from baseline at anytime during therapy:
    - > 10 mmHg

Statistical Analysis Plan	
Status: Final Version 1.0	Revised: 09Jun2020

- >15 mmHg
- >20 mmHg
  - Number of subjects with PASP>35 mmHg at anytime during therapy
- Right ventricular outflow tract (RVOT) acceleration time (will be used only as confirmatory variables for pulmonary hypertension)
  - Mean Change from Baseline in RVOT (msec) by visit
  - Number of subjects with Baseline  $\geq$ 100 msec and at EOS/ET RVOT <100 msec
  - Number of subjects with any RVOT measurement < 100 msec post-baseline

Summary of the number of ECHOs per subject will also be presented.

### 2.3.2.3 Heat Maps

Heat maps will be constructed for all valve scores to visualize longitudinal changes, if any, in regurgitation measures in individual subjects over time. An example of a heat map is shown below.

Dosing	Subjects	Visit 1	Visit 8	Visit 12
Placebo	2 subjects	Absent	Absent	ECHO
Placebo	5 subjects	Absent	Trace	Trace
Placebo	1 subject	Absent	Mild	Trace
ZX008 0.2 mg/kg/day	4 subjects	Absent	Absent	Absent
....				

Note: different colors represent the valve scores such as No ECHO, Absent, Absent, Mild, Moderate, and Severe.

## 2.4 Study Population

Male and female subjects, aged 2 to 18 years of age with a medical history and clinical diagnosis of Dravet syndrome who meet other eligibility criteria could be enrolled in the study. This section includes the inclusion and exclusion criteria related to cardiac safety.

### 2.4.1 Inclusion Criteria Related to Cardiac Safety

No inclusion criteria were related to cardiac safety.

### 2.4.2 Exclusion Criteria Related to Cardiac Safety

Subjects must not meet any of the following criteria to be eligible for study participation:

- Subject has Pulmonary Arterial Hypertension (PAH)
- Subject has current or past history of cardiovascular or cerebrovascular disease, such as cardiac valvulopathy, myocardial infarction or stroke.
- Subject is receiving concomitant therapy with: centrally-acting anorectic agents; monoaminoxidase inhibitors; any centrally-acting compound with clinically appreciable amount of serotonin agonist or antagonist properties, including serotonin reuptake inhibition; atomoxetine, or other centrally-acting noradrenergic agonist; cyproheptadine, and/or cytochrome P450 (CYP) 2D6/3A4/2B6 inhibitors/substrates. (Note: Short-term medication requirements will be handled on a per case basis by the Medical Monitor.)
- Subject does not have a cardiovascular or cardiopulmonary abnormality based on ECHO, ECG or physical examination, including but not limited to trace mitral or aortic valve regurgitation or signs of

Statistical Analysis Plan	
Status: Final Version 1.0	Revised: 09Jun2020

pulmonary hypertension, and is approved for entry by the central cardiac reader.

### 2.4.3 Sample Size

No formal sample size calculations were conducted related to cardiac safety for Study 2. Study 2 includes all subjects enrolled in ZX008-1501 and ZX008-1502 except the first 119 subjects which comprise Study 1.

## 2.5 Randomization and Blinding

Each subject was randomized in a 1:1:1 fashion and receive one of the following treatments:

- A. 0.2 mg/kg/day ZX008
- B. 0.8 mg/kg/day (up to 30 mg/day) ZX008
- C. Placebo

Neither the subjects nor the investigator knew which treatment is being administered.

## 3. Cardiac Safety Data Collection and Analysis

### 3.1 ECG Assessment

#### 3.1.1 Equipment

Twelve-Lead Electrocardiograms were collected on a Mortara ELI-150c ECG machine (Milwaukee, WI) located at each clinical site.

#### 3.1.2 Transfer of ECGs

Electrocardiograms were digitally transferred to ERT for analysis.

#### 3.1.3 Collection of ECGs

The clinical ECG database will be derived from 12-lead ECGs collected from the ELI-150c ECG machines.

Single, 12-lead ECGs were collected at Screening, Baseline (Visit 3), Week 6 (Visit 8), and Week 14 (Visit 12). ECGs were collected after the subjects had been in supine position resting for  $\geq 5$  minutes.

The time of the ECG was not controlled.

#### 3.1.4 Definition of Baseline

The baseline for this study will be the data collected from the ECG taken at Baseline (Visit 3).

#### 3.1.5 Variables Measured

At the central laboratory, using CAMI software (or equivalent), the cardiac technician will annotate the Global Superimposed Median Beat (GSMB).

The following variables will be measured or calculated on each ECG:

- QRS duration
- PR interval
- Heart rate (10 second average)
- QT
  - The QT interval will be measured from the earliest detection of depolarization in any lead (beginning of the Q or R wave) to the latest detection of repolarization in any lead (end of the T-wave).
- QTcF

The RR interval will be reported, from which the corrected QT interval (QTc) using Fridericia's formula (QTcF) will be calculated.

Fridericia's correction:  $QTcF = \frac{QT}{RR^{1/3}}$  where QT, RR, and QTcF are expressed in seconds.

Statistical Analysis Plan	
Status: Final Version 1.0	Revised: 09Jun2020

For convenience, QT, RR, PR, QRS, and QTcF will be shown in milliseconds (ms) in the tables, figures and listings.

### 3.1.6 Clinical Analysis of ECGs

The over-reading cardiologist will give a clinical interpretation for each ECG at each time point. These will be presented in the data listing provided at the end of the study. Each ECG will be classified as Normal (N), Abnormal Clinically Insignificant (ACI), or Abnormal Potentially Clinically Significant (APCS).

### 3.1.7 Non-Digital ECG Evaluation

Data not acquired using the ECG equipment provided by ERT will not be eligible for centralized reading, nor will it be included in the database.

## 3.2 Echocardiographic Analysis

### 3.2.1 Equipment

Site-owned equipment was used for the collection of echocardiograms.

Prior to being qualified for subject enrollment, all echocardiographers were required to participate in a WebEx PowerPoint training presentation and transferred test data to BMS. The WebEx session consisted of reviewing protocol specific views, study related forms and the process of uploading the images through web portal.

Each echocardiographer was required to submit a certification ECHO. The certification ECHO was performed on a non-study participant. The participating ECHO facility was informed during the training session that they would not be able to perform ECHOs on true study subjects until they received a "passed" Certification ECHO Evaluation Form.

### 3.2.2 Transfer of Echocardiograms

Electrocardiograms were either digitally transferred or copied to CD and sent via courier to ERT for analysis.

### 3.2.3 Collection of Echocardiograms

ECHOs were taken at Screening, Week 6 (Visit 8), and Week 14 (Visit 12). For each ECHO, cardiac technicians check to make sure the Nyquist Limit (color scale) was set between 60 cm/s and 80 cm/s. All sonographers at the study sites submitted a certification ECHO before study ECHOs were obtained.

The time of the ECHO was not controlled.

### 3.2.4 Definition of Baseline

The baseline for this study will be the data collected from the ECHO taken at Screening.

### 3.2.5 Variables Measured

Echocardiograms were evaluated by two cardiologists using DigiView software. Details of the assessment and adjudication process are available in the ECHO operations manual for these studies.

In addition to assessing each valve (Mitral, Aortic, Tricuspid, and Pulmonary) for regurgitation, the following variables were measured or calculated on each ECHO:

- Right Ventricular Outflow Tract Acceleration Tim (RVOT)
- Pulmonary Artery Systolic Pressure (PASP)
- Pulmonic Valve Peak Regurgitation Jet Velocity (PVPR)

### 3.2.6 Clinical Analysis of ECHOs

Each ECHO was read, independently by two physicians. A third physician was assigned as an adjudicator. The adjudicator read the ECHO if the any of the following discrepancies occurred between the first and second reader:

- Aortic valve findings were not identical
- Mitral valve findings were not identical
- LVFS difference between the two physicians was >5%
- LVEF difference between the two physicians was >10%

Statistical Analysis Plan	
Status: Final Version 1.0	Revised: 09Jun2020

- PASP difference between the two physicians was >10 mmHg
- Clinical significance between the two readers was not identical

The adjudicator chose which of the two readings was the final reading.

### 3.2.7 Alert Criteria

Echocardiographic alert criteria included:

- Valve regurgitation (aortic or mitral)
- $\geq$  moderate valve regurgitation (tricuspid or pulmonic)
- Mean mitral valve gradient  $\geq$  4 mmHg
- Mean aortic valve gradient  $\geq$  15 mmHg
- Mean tricuspid valve gradient  $\geq$  4 mmHg
- Peak pulmonic valve gradient  $\geq$  21 mmHg
- Tricuspid regurgitation jet velocity > 2.8 meters/sec with or without the findings OR
- One of the following findings in the absence of being able to measure tricuspid regurgitation jet velocity:
  - Change in right ventricle/left ventricle basal diameter ratio > 1.0
  - Right ventricular outflow tract flow acceleration time < 100 msec
  - Dilatation of the inferior cava vein (diameter > 21mm and <50% inspiratory collapse) and/or right atrial dilatation
  - Change in the geometry of the interventricular septum in systole (flattening) with left ventricular eccentricity index >1.1 in systole and/or in diastole
  - Early diastolic pulmonary regurgitation velocity >2.2 m/sec
  - Tricuspid Annular Plane Systolic Excursion below 18 mm or below Z-score – 2

## 4. Statistical Analysis

The statistical analyses of the cardiac safety data are designed to assess the potential toxicity of ZX008 when administered for up to 14 weeks as adjunctive treatment for children and young adults with Dravet syndrome.

### 4.1 General Principles and Considerations

This section describes the algorithms and conventions that will generally apply to program analyses and to the formatting of the data, as required to perform the proposed summary tabulations and to create the individual subject data listings. Unless otherwise indicated, these specifications will apply to all analyses. For details on the tables and figures that will be created, please refer to Section 5, Tables, Figures, and Listings.

The statistical analysis will be reported using summary tables, figures, and data listings.

ECG and ECHO variables at each time point will be obtained. Changes from baseline will be calculated and compared for each of 0.2 and 0.8 mg/kg/day treatment groups to placebo. The primary outcome is the assessment for the development of valvular heart disease and pulmonary arterial hypertension.

Continuous variables will be summarized using descriptive statistics (i.e., total number [n], mean, standard deviation [SD], minimum, maximum, and 95% CI). Results will be presented to one or two decimal places for means and SD, as appropriate.

Qualitative variables will be presented as category counts and percentages. Percentages will be presented to one decimal place.

All dates will be displayed in DDMMMYYYY format (e.g., 15DEC2012).

All analyses will be carried out using SAS® Version 9.4 or higher.

### 4.2 Analysis Population

ECG and ECHO data will be analyzed using a Safety Population, including all randomized subjects who received at least one dose of study medication in Study 2, excluding the 119 subjects in Study 1.

Statistical Analysis Plan	
Status: Final Version 1.0	Revised: 09Jun2020

As there are few subjects per site, no comparisons between sites will be conducted.

#### 4.2.1 Handling of Missing Data

All data available will be used for the analysis. Missing data points will not exclude the rest of the subject's data from analysis, and missing data will not be imputed.

#### 4.3 Interim Analysis

No interim analysis is scheduled for this trial.

#### 4.4 Multiplicity Adjustments

No adjustments for multiplicity will be made for the primary cardiovascular endpoint.

#### 4.5 Primary Analyses

##### 4.5.1 Electrocardiogram

The primary ECG objective is to evaluate the effect of ZX008 0.8 mg/kg/day (max 30 mg/day) on QTcF.

The primary analysis of the QTcF is the mean baseline-adjusted difference between treatment and placebo and will be performed using an analysis of variance (ANOVA) for each post-dose time point. The ANOVA model will include a fixed effect for treatment. The upper bound of the one-sided 95% CI (or, equivalently, two-sided 90% CI) of the mean baseline-adjusted difference between treatment and placebo QTcF ( $\Delta\Delta\text{QTcF}$ ) will be calculated from the ANOVA for each time point.

The general formula to calculate the  $\Delta\Delta\text{QTcF}$  at the  $i$ th timepoint is:

Mean  $\Delta\Delta\text{QTcF}_i = \text{Mean } \Delta\text{QTcF}_i \text{ for the active group} - \text{Mean } \Delta\text{QTcF}_i \text{ for the placebo group}$ , based on the ANOVA model, where  $i =$  at  $i$ th timepoint and  $\Delta\text{QTcF}_{ti} = \text{QTcF}_{ti} \text{ on Day } 1 - \text{QTcF}_{ti} \text{ at Baseline (i.e., Day - 1)}$ , where  $ti =$  at  $i$ th time point for subject  $t$

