### 2.5. Determination of Sample Size

The sample sizes for Zogenix Studies 1501 and 1502 were calculated based on the results of two trials with stiripentol reported in the European Public Assessment Report (EPAR) for stiripentol (EMA, 2007). The stiripentol EPAR summarizes the results from two studies: STICLO France and STICLO Italy. In the stiripentol groups, the standard deviation (SD) of the percentage change in seizure frequency from baseline to month 2 was 42% in the French trial and 26% in the Italian trial. The analogous SDs for placebo groups were 38% and 62%. An SD of 50% was assumed for the primary analysis in Protocols 1501 and 1502 that compares ZX008 0.8 mg/kg/day to placebo on the change from baseline in seizure frequency. Using a two-sided test at the  $\alpha=0.05$  significance level, a sample size of 35 subjects per treatment group affords 90% power to detect a difference in mean change from baseline of 40 percentage points. Similar assumptions and calculations yielded a requirement for an additional 35 subjects in the 0.2 mg/kg/day ZX008 group. The total sample size for each study was therefore set at 105 subjects.

In December 2016 results from a double-blind, placebo-controlled Phase 3 study with Epidiolex® (cannabidiol) to treat seizures in Dravet syndrome were presented at the American Epilepsy Society Meeting (<http://ir.gwpharm.com/events.cfm>). In the Epidiolex study, active drug reduced seizures by 39% compared to a reduction of 13% in the placebo. Review of the data suggested that the standard deviation was relatively large, likely above 50% in both treatment groups. In consideration of this new data, the sample size was re-estimated for the ZX008 studies to assume a SD of 55%, higher than the previous estimate of 50%. Other assumptions in the sample size calculation remained unchanged. A sample size of approximately 120 subjects (40 per arm) affords 90% power to detect a difference in mean change from baseline of 40 percentage points with 55% SD. Considering the variability seen in the STILCO and Epidiolex trials, the sample size for Study 1 and Study 2 is set at 120 subjects, 40 per treatment arm. Note that the change in assumed SD was based entirely on data from external trials. Efficacy data from both Study 1501 and 1502 are still blinded and were not used in re-estimating the required sample size.

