### 10.6. ECG

12-Lead ECGs data (PR, QRS, QT, QTcF, and HR) will be documented for subjects during study at baseline (Visit 1 and Visit 3), Day 43 (Visit 8), at End of Study (Visit 12) and at Cardiac Follow-up (Visit 14).

Analysis of Echocardiograms will be included in a separate report from ERT.

This document is confidential.

All ECG values will be presented in the subject data listing. In addition to the subject data listing with all ECG values, a listing of all abnormal, clinically relevant findings will be presented organized by subject, by parameter, then by visit.

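### Free improvement: QTcF change is analysed with treatment as the only model term; adding Visit 3 QTcF as a covariate would usually tighten the safety bound at almost no cost

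*SAP*

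**What the plan says.** The two cardiovascular SAPs use the same wording for the primary QTcF analysis in Section 4.5.1. It is an ANOVA for each post-dose time point, and its model is described in one sentence: "The ANOVA model will include a fixed effect for treatment". The term baseline-adjusted in that section does not mean a covariate. The formula that follows defines the estimate as mean change on active minus mean change on placebo. The statistic reported is the upper limit of a one-sided 95% interval.

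Section 3.1.4 fixes the reference value: "The baseline for this study will be the data collected from the ECG taken at Baseline (Visit 3". Section 3.1.3 lists the tracings: "Single, 12-lead ECGs were collected at Screening, Baseline (Visit 3), Week 6 (Visit 8), and Week 14 (Visit 12". So there are two pre-dose and two post-dose ECGs, and the QTcF change uses one of the pre-dose pair. Section 3.1.3 adds that the time of the ECG was not controlled.

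Section 5 of the Study 2 cardiovascular SAP lists ANOVA-based upper bounds for QTcF (Tables 1.1.1 to 1.1.5), heart rate (1.2.x), QRS (1.3.x) and PR (1.4.x). All are split by age or by age and sex. On precision, Section 2.4.3 of that SAP says: "No formal sample size calculations were conducted related to cardiac safety for Study 2".

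**The concern.** A change score from one tracing carries all the noise of that tracing. Unless the pre-dose and post-dose values are almost perfectly correlated, subtracting the whole baseline removes too much, and a regression on baseline leaves less residual variance. The efficacy analysis of the same subjects does use the baseline value as a covariate: main SAPs, Section 6.3.1.1 for Study 1 and Section 8.1 for Study 2. The ECG analysis does not, and gives no reason.

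What is at stake is the precision of the one number the plan offers on QTcF, and its sensitivity to a chance difference between arms at Visit 3. Because no cardiac sample size was set, whatever precision the data allow is all there is.

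**Working it through.** **Inputs from the documents.** The model has treatment only (4.5.1), the baseline is a single Visit 3 ECG (3.1.4), the bound is one-sided 95%, and there are three arms randomised 1:1:1. The only source for the number per arm is the efficacy calculation in Section 2.5 of the Study 2 main SAP: "A sample size of approximately 120 subjects (40 per arm) affords 90% power".

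**Reproducing the plan's figures.** For a difference of 40 points, SD 55 and two-sided alpha 0.05, n = 2 x (1.960 + 1.282)^2 x 55^2 / 40^2 = 39.7. This rounds up to 40 per arm, with power 90.2%. The stated equivalence of a one-sided 95% and a two-sided 90% limit also holds, since both use z = 1.645.

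**Inputs that are assumptions.** The documents give neither the SD of QTcF nor rho. I take SD s = 15 ms for a single reading and rho = 0.5, 0.7 and 0.9, with equal variances. The percentage gains do not depend on s. The 4.5.1 formula writes the post-dose value as Day 1, but no Day 1 ECG is listed, so I read it as Visit 8 or Visit 12.

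**Formulas, relative to s^2.**
- Change from Visit 3, treatment only: 2(1 - rho).
- The same with Visit 3 QTcF as covariate: 1 - rho^2.
- Ratio of standard errors: sqrt((1 + rho)/2).
- Half-width = t(0.95, df) x s x sqrt(variance x 2/n), with df 117 without the covariate and 116 with it, and t about 1.658 in both cases.

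Example at rho 0.5. As planned: 1.658 x 15 x sqrt(1.00 x 2/40) = 5.56 ms. With the covariate: 1.658 x 15 x sqrt(0.75 x 2/40) = 4.82 ms.

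| rho | As planned (ms) | With Visit 3 covariate (ms) | Narrower by |
|---|---|---|---|
| 0.5 | 5.56 | 4.82 | 13% |
| 0.7 | 4.31 | 3.97 | 8% |
| 0.9 | 2.49 | 2.42 | 3% |

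**Smaller cells.** Simulated mean half-width ratios (covariate / as planned, 2,000 runs each) at rho 0.5, 0.7 and 0.9 were:
- 40 per arm: 0.869, 0.926, 0.979.
- 25 per arm: 0.872, 0.930, 0.981.
- 7 per arm: 0.894, 0.950, 1.007.

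The 25 and 7 are assumed sizes, since the documents give no subgroup counts. At 7 per arm and rho 0.9 the gain is gone.

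**Chance imbalance.** If the active arm starts d higher, its post-dose mean is expected to be rho x d higher. Subtracting d leaves a shift of -(1 - rho)d. One standard error of the baseline difference is 15 x sqrt(2/40) = 3.4 ms, which gives shifts of 1.7, 1.0 and 0.3 ms at rho 0.5, 0.7 and 0.9. A high active baseline makes the drug look safer, and a low one makes it look worse. The covariate removes this shift.

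**The Screening ECG.** If Screening correlates with the post-dose value as strongly as Visit 3 does, using the mean of both as covariate gives standard-error ratios of 0.82, 0.84 and 0.86. If its correlation with post-dose and with Visit 3 is 0.5, against 0.7 between Visit 3 and post-dose, simulation at 40 per arm gives 0.934 for the mean of the two. Visit 3 alone gives 0.925, and both ECGs as separate covariates give 0.901. A plain average can therefore be slightly worse than Visit 3 alone.

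**The case against.** The strongest reply is that nothing here is invalid. That stands. Randomisation makes the expected baseline difference zero, so the change score is unbiased for the arm difference and the bound has its stated coverage. A reader might infer that baseline imbalance goes uncorrected, or that regression to the mean biases the comparison. The documents support neither. The 4.5.1 formula subtracts baseline, so it over-corrects a chance difference, and regression to the mean affects individuals in all arms alike.

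It can also be said that no decision turns on this. That stands too: no QTcF margin or pass rule is given. Section 4.1 of the Study 2 cardiovascular SAP names valvular heart disease and pulmonary arterial hypertension as the primary outcome, and its introduction reports a dedicated QTc study without a significant effect. A wide upper bound errs on the cautious side.

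The widths at 40 per arm match no listed Study 2 QTcF ANOVA table, because Tables 1.1.1 to 1.1.5 are all subgroups. They illustrate the percentages and do not forecast an output.

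Two further remedies are tempting and do not hold up:
- **An age factor (<6, >=6 years) in every model.** It has a single level in every listed heart rate, PR and QRS table and in QTcF Tables 1.1.2 and 1.1.3, so it cannot be estimated there.
- **Averaging Screening into the baseline.** This departs from the last-value rule of the main SAPs (Study 1, 6.1.4; Study 2, 6.2). It also uses a tracing about six weeks older, from a visit at which eligibility is assessed. It is a trade-off, not a correction.

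What survives is that Visit 3 QTcF is already in hand and unused as a covariate.

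**Conclusion.** The point holds as an efficiency improvement, not as an error. Both cardiovascular SAPs plan a valid but usually less precise analysis than the same data allow. The size rests on an assumed rho: about 13%, 8% or 3% off the half-width at rho 0.5, 0.7 or 0.9 with 40 per arm, less in the subgroup tables, and possibly nothing in very small cells at high rho. The millisecond figures rest also on an assumed SD of 15 ms. The covariate further removes a chance shift of about -(1 - rho)d. The documents do not show that any safety conclusion would differ.

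**What to change.** In Section 4.5.1 of both cardiovascular SAPs, replace the ANOVA with a per-visit ANCOVA of change in QTcF on treatment and Visit 3 QTcF. Report each active-minus-placebo difference in adjusted means with its one-sided 95% upper bound. Use the same form for heart rate, PR and QRS, each with its own Visit 3 value as covariate.

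Include an age term only where the analysed subjects span more than one age level, not in the age-specific tables. Keep Visit 3 as the primary baseline. If the Screening ECG is to be used, enter it as a second covariate in a supportive analysis.

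The cost is a few lines of SAP text and one model term per table. No new data are needed, and no subject is lost, because a change from Visit 3 already requires the Visit 3 value.
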